2 CLINICAL PROTOCOL SYNOPSIS

Compound No.: E7438

Name of Active Ingredient: Tazemetostat (INN)

Study Protocol Title

A Phase 2 Study of Tazemetostat in Relapsed or Refractory B-cell Non-Hodgkin's Lymphoma with EZH2 Gene Mutation

Investigators

Refer to the Attachment separately provided to each site.

Sites

Study centers: Approximately 30 sites (planned)

Study location: Japan

Study Period and Phase of Development

Study period: 30 months (planned) Phase of development: Phase 2

(Note: subjects who meet approved indication of E7438 in Japan will continue this study as a post-

marketing study.)

Objectives

Primary objective

To assess the efficacy of tazemetostat in patients with relapsed or refractory B-cell non-Hodgkin's lymphoma (NHL) below by objective response rate (ORR).

Cohort 1: Follicular lymphoma (FL) with EZH2 gene mutation

Cohort 2: Diffuse large B-cell lymphoma (DLBCL) with EZH2 gene mutation

Secondary objectives

- (1)To assess the efficacy of tazemetostat by the endpoints below.
 - ·Progression-free survival (PFS)
 - ·Duration of response (DOR)
 - ·Time to response (TTR)
- (2)To assess the safety of tazemetostat.

Exploratory objectives

- (1)To explore the pharmacokinetics (PK) of tazemetostat.
- (2)To explore the frequency of EZH2 gene mutation in B-cell NHL.

Study Design

This is a multicenter, open-label, phase 2 study in relapsed or refractory B-cell NHL patients with EZH2 gene mutation, consists with 2 cohorts. The study will assess efficacy and safety of tazemetostat in FL patients with EZH2 gene mutation in cohort 1, and DLBCL (including primary mediastinal B-cell lymphoma and transformed FL) patients with EZH2 gene mutation in cohort 2.

This study will be conducted in the following 3 phases: Pre-treatment Phase, Treatment Phase, and Follow-up Phase.

The Pre-treatment Phase consists of Screening 1, Screening 2, registration, and baseline assessment.

Eisai Confidential Page 2 of 71

In Screening 1, the EZH2 gene mutation will be confirmed at central laboratory in patients with histologically diagnosed as FL (cohort 1) or DLBCL (cohort 2) who are available to provide archival tumor sample (Inclusion Criteria 1) and not apparent to conflict other eligible criteria to participate in the study. The archival tumor samples will be submitted to the central laboratory, and then this will be reported to the sponsor. If EZH2 gene mutation was confirmed, conduct Screening 2 to confirm the other eligibility for study treatment. Obtain the written informed consent with regards to tumor EZH2 gene mutation test and study treatment respectively, before Screening 1 and Screening 2. Screening 2 will last no longer than 28 days before the start of study treatment. After screening assessments, the patient who meets the inclusion criteria and does not meet the exclusion criteria will be enrolled. The baseline assessment will be conducted within 3 days before the treatment in order to confirm that the patient continues to meet the inclusion criteria and does not meet the exclusion criteria before moving to the Treatment Phase.

The Treatment Phase consists of 28 days/cycle for tazemetostat 800 mg twice daily (BID) oral administration (1600 mg total daily dose) on a continuous basis and lasts until discontinuation of study drug. Subjects will discontinue study drug at the time of disease progression (site evaluation), development of unacceptable toxicity, subject's request to discontinue, withdrawal of consent, or study termination by the sponsor.

Follow-up Phase consists of the evaluation at discontinuation which is performed within 7 days after the discontinuation of the study and a final observation which occurs 30 days (+7 days) after final administration of tazemetostat or initiation of a new anti-tumor therapy, whichever occurs early.

Number of Subjects

FINAL: 29 Jan 2021

Cohort 1: FL with EZH2 gene mutation Eight efficacy evaluable patients (planned) Cohort 2: DLBCL with EZH2 gene mutation Thirteen efficacy evaluable patients (planned)

Eisai Confidential Page 3 of 71

Eisai Confidential Page 4 of 167

Inclusion Criteria

- (1) Patient with histological diagnosis of B-cell NHL as follows, who has provided written consent to submit archival tumor sample to central laboratory to confirm the EZH2 gene mutation status in tumor:
 - · Cohort 1: Follicular lymphoma (FL)
 - · Cohort 2: Diffuse large B-cell lymphoma (DLBCL) (including primary mediastinal B-cell lymphoma and transformed FL)
- (2) Patient who has confirmed EZH2 gene mutation of tumor in central laboratory
- (3) Patient who has measurable disease as below:
 - · Lymph node or ex-nodal disease diagnosed by CT scan
 - · Clearly measurable in 2 orthogonal ways by CT scan
 - $\cdot \ge 1.5$ cm in long axis or >1.0 cm in short axis, when long axis were <1.5 cm
- (4) Patient who had previous therapy with systemic chemotherapy and/or antibody therapy and for which no standard therapy exists
- (5) Patient who was progressive disease (PD) or did not have response (complete response [CR] or partial response [PR]) in previous systemic therapy, or relapsed or progressed after previous systemic therapy
- (6) Patient with Eastern Cooperative Oncology Group (ECOG) performance status of 0 to 1
- (7) Patient with life expectancy of ≥ 3 months from starting study drug administration
- (8) Patient with adequate renal function:
 - · Serum creatinine $\leq 1.5 \times$ upper limit of normal (ULN)
- (9) Patient with adequate liver function:
 - · Total bilirubin <1.5×ULN
 - · Aspartate aminotransferase (AST) and alanine aminotransferase (ALT) ≤3.0×ULN
- (10) Patient with adequate bone marrow function:
 - (confirm 2 weeks or later from last administration of granulocyte colony-stimulating factor [G-CSF] and blood transfusion, if these are used)
 - · Absolute neutrophil count $\geq 1.5 \times 10^3 / \mu L$ ($\geq 1.5 \times 10^9 / L$)
 - · Platelet count $\geq 10.0 \times 10^4 / \mu L$
 - · Hemoglobin ≥9.0 g/dL
- (11) Patient with time between prior anti-tumor therapy and first administration of study drug as below:
 - · Cytotoxic chemotherapy At least 3 weeks
 - · Non-cytotoxic chemotherapy (eg., corticosteroids*, small molecule inhibitor) At least 2weeks
 - · Monoclonal antibody (ies) At least 4 weeks
 - · Radiotherapy
 - -At least 3 weeks from radiation therapy
 - -At least 6 weeks from prior radioisotope therapy
 - · Autologous hematopoietic stem cell transplantation At least 6 months
 - *: Patient may receive no more than 10 mg of prednisolone daily or equivalent corticosteroid when used for treatment of lymphoma-related symptoms.
- (12) Patient with no carry-over of \geq Grade 2 adverse events of the prior treatment that may affect the safety evaluation of the investigational drug
- (13) Male and female patient ≥20 years of age at the time of informed consent
- (14) Patient who has provided written consent to participate in the study

Eisai Confidential Page 4 of 71 FINAL: 29 Jan 2021

Exclusion Criteria

- (1) Patient with prior exposure to EZH2 inhibitor
- (2) Patient with a history or a presence of central nerves invasion
- (3) Patient with malignant pleural effusion, cardiac effusion, or ascites retention
- (4) Patient with allogeneic stem cell transplantation
- (5) Patient with a medical need for the continued use of potent inhibitors of CYP3A, or potent inducer of CYP3A (including St. John's wort). Patient is eligible if 2 weeks or longer have passed since the last use of such agents prior to the first dose of study drug.
- (6) Patient unwilling to exclude grapefruit (juice) from the diet for 1 week prior to study drug administration and throughout the study
- (7) Patient with the inability to take oral medication, or malabsorption syndrome or any other uncontrolled gastrointestinal condition (eg, nausea, diarrhea, or vomiting) or medical history (eg, gastrectomy or enterectomy) that might impair the bioavailability of study drug
- (8) Patient with significant cardiovascular impairment
 - 1) History of congestive heart failure of ≥ New York Heart Association (NYHA) Class III
 - 2) Uncontrolled arterial hypertension, unstable angina, myocardial infarction, or stroke within 6 months of the first dose of study drug
 - 3) Ischemic heart disease, cardiac arrhythmia requiring medical treatment
- (9) Patient with prolongation of corrected QT interval using Fridericia's formula (QTcF) to >480 msec
- (10) Patient with venous thrombosis or pulmonary embolism within the last 3 months before starting study drug
- (11) Patient with complications of hepatic cirrhosis, interstitial pneumonia or pulmonary fibrosis
- (12) Patient with active infection requiring systemic therapy
- (13) Patient with known hypersensitivity to any component of study drug
- (14) Patient who is positive for HIV antibody, HCV antibody, and HCV-RNA, or HBs antigen. Patient who is positive for HBs or HBc antibody and showing DNA more than sensitivity in HBV-DNA assay
- (15) Patient with malignancy of activity other than B-cell NHL within 36 months before informed consent (except treated non-invasive melanoma, basal cell carcinoma of the skin or squamous cell carcinoma, intraepithelial carcinoma such as uterine cervix).
- (16) Women of childbearing potential or man of impregnate potential who don't agree that both the patient and his/her partner will use a medically effective method for contraception (as the below note) for periods from before informed consent to during the clinical study and 30 days later (for males 90 days later) from last administration of study drug.
- (17) Woman who is pregnant or breastfeeding (not eligible even if she discontinues breastfeeding)
- (18) Patient who was decided as inappropriate for medical or other reasons to participate in the study by the investigator or sub-investigator
- (19) Patient who has a prior history of myeloid malignancy including T-cell lymphoblastic lymphoma, T-cell acute lymphoblastic leukemia or myelodysplastic syndrome

Note: Condom*, contraceptive sponge**, foam**, jelly**, diaphragm*, intrauterine device (IUD)*, or use of oral contraception* from at least 30 days before starting the study treatment

Eisai Confidential Page 5 of 71

(*Approved drugs or certified medical devices in Japan, **Non-approved drugs or certified medical devices in Japan)

Study Treatment

Tazemetostat 800 mg BID (1600 mg total daily dose) will be administered orally by continuous regimen, no less than 8 hours between doses.

Tazemetostat will be provided as 200 mg tablet.

Tazemetostat Dose Reduction and Interruption Instructions

Dose reduction and interruption for subjects who experience tazemetostat-related toxicity will follow the instructions shown in Table below. Dose reductions will be based on the previous dose level in order of 600, 400 mg BID (1200 mg, 800 mg total daily dose, respectively). Once the dose is reduced, it cannot be increased at a later date. Any dose adjustment must be discussed with the sponsor or discontinue tazemetostat when toxicities requiring dose reduction occur at the dose of 400 mg BID.

If a subject experiences myeloid malignancy including myelodysplastic syndrome, study treatment should be interrupted and restart (including dose modification)/discontinuation of study treatment should be discussed with the sponsor. If a subject experiences T-cell lymphoblastic lymphoma/T-cell acute lymphoblastic leukemia, study treatment should be discontinued and other actions should be discussed with the sponsor.

Study treatment may be interrupted, if it is required to ensure the safety of a subject experiencing an adverse event that is unrelated to the study drug. In such cases, study treatment should be resumed as soon as possible, at the same dose.

Tazemetostat Dose Reduction and Interruption Instructions

Tazemetostat-rel	lated Toxicity	During Therapy ^d	Dose adjustment ^d
Grade 1 and Tol	erable Grade 2ª	Continue tazemetostat	Maintain dose level
Intolerable Grad Grade 3 ^b	le 2ª and	Interrupt tazemetostat until resolved to Grade ≤1 or baseline ^e	Dose reduction by one dose level
Grade 3 and	ANC ≥0.75×10 ⁹ /L	Continue tazemetostat	Maintain dose level
Grade 4 neutropenia	ANC <0.75×10 ⁹ /L	Interrupt tazemetostat until resolved to ANC≥0.75×10 ⁹ /L ^e	Dose reduction by one dose level
Grade 4 ^c	•	Interrupt tazemetostat until resolved to Grade ≤1 or baseline ^c	Discuss with the sponsor or discontinue tazemetostat

ANC = absolute neutrophil count.

FINAL: 29 Jan 2021

- a: Tolerability of Grade 2 toxicities will be judged by the investigator or subinvestigator.
- b: Dose interruption and reduction are not necessary for Grade 3 thrombocytopenia, anemia and Grade 3 or 4 leukopenia, lymphopenia and laboratory abnormalities that are not clinically relevant. Initiate optimal medical management for nausea, vomiting, and/or diarrhea prior to any study treatment interruption or dose reduction and follow the dose reduction and interruption instructions when it cannot be controlled.
- c: Laboratory abnormalities judged to be non-life threatening, will be excluded and managed as Grade 3.
- d: Discuss with the sponsor when to consider the dose interruption and adjustment other than the instructions.
- e: To minimize the duration of interruption, assessment at least every 7 days is recommended. A delay of tazemetostat for more than 28 days due to any toxicity that is related to the study treatment must be discussed with the sponsor before treatment can be resumed.

Eisai Confidential Page 6 of 71

Eisai Confidential Page 7 of 167

Duration of Treatment

Treatment will continue until disease progression (site evaluation), development of unacceptable toxicity, subject's requests to discontinue, withdrawal of consent, or study termination by the sponsor.

[Subjects who meet approved indication of tazemetostat in Japan]

As per regulatory requirements in Japan, from the time tazemetostat is approved by the regulatory authority, these subjects will continue this study as a post-marketing study. Treatment will continue until tazemetostat is commercially available for individual subjects at each study site, at which time the subjects will be switched to commercial tazemetostat.

Concomitant Drug/Therapy

The following drugs and therapies are prohibited from the time of subject enrollment to final study drug administration:

- · Anti-tumor therapies (Subjects may receive corticosteroid for local or systemic symptom control prior to and while on study. Starting study drug treatment however, subjects may receive no more than 10 mg of prednisolone daily or equivalent corticosteroid when used for treatment of lymphoma related symptoms)
- · Any agent that potently inhibits or induces CYP3A
- · Other investigational agents

Assessments

Efficacy Assessments

Efficacy assessment will be performed by investigator or subinvestigator based on "Revised response criteria for malignant lymphoma (IWG-2007)" (Cheson, et al., 2007). Overall response and best overall response (BOR) (best response recorded at the designated visits during the study) will be assessed. Perform the assessment below for tumor assessment.

CT scans will be performed at Screening 2, every 8 weeks from study drug administration up to first 32 weeks, then every 12 weeks and at discontinuation.

PET scans will be performed at Screening 2. If positive, perform when it is required to confirm CR as soon as possible or when clinically indicated.

If gastrointestinal disease is suspected, endoscopic examination will be performed at Screening 2. If exists, perform when it is requested to confirm CR as soon as possible or when clinically indicated.

To evaluate bone marrow infiltration, a bone marrow aspiration or biopsy will be performed at Screening 2. If positive or indeterminate, perform when it is requested to confirm CR as soon as possible or when clinically indicated.

Also, central review will be conducted by the Imaging Review Committee for CT and PET assessment which is obtained within 24 months after the last subject's enrollment (cut-off date: 02 Dec 2020). In addition, Efficacy and Safety Evaluation Committee (ESEC) will conduct central evaluation based on the review of Imaging Review Committee and other assessment / bone marrow infiltration evaluated by the investigator or subinvestigator, to determine the overall responses and the best overall response.

The primary endpoint and the secondary endpoint with regard to efficacy are defined as below, and will be evaluated by the result of ESEC review.

ORR:

The rate of subjects whose BOR is CR or PR.

Eisai Confidential Page 7 of 71 FINAL: 29 Jan 2021

Eisai Confidential Page 8 of 167

PFS:

Defined as the term between the date of administration of the first dose of the study drug and the date of the first event (PD or death whichever occurs first). The detail of the censoring rule for PFS will be described in the statistical analysis plan (SAP).

DOR:

Defined as the term between the date of confirmation of the first response and the date of confirmation of the PD. The detail of the censoring rule for DOR will be described in the SAP.

TTR·

Defined as the term between the date of administration of the first dose of the study drug and the date of confirmation of the first response.

Pharmacokinetics Assessments

To measure plasma trough concentrations of tazemetostat.

Biomarker Assessments

At Screening 1, archival tumor samples (formalin-fixed paraffin-embedded: FFPE) will be submitted to the central laboratory for detection of EZH2 gene mutation status in patients with written informed consent for tumor EZH2 gene mutation test.

Safety Assessments

Safety assessments will consist of monitoring and recording all adverse events (AEs) and serious adverse events (SAEs); periodic clinical laboratory assessment; measurement of vital signs, 12-lead electrocardiograms (ECGs), ECOG-PS, and physical examinations. Severity will be evaluated by grading of Common Terminology Criteria for Adverse Events (CTCAE v4.03).

Bioanalytical Methods

Plasma concentrations of tazemetostat will be measured by validated methods using liquid chromatography with tandem mass spectrometry (LC-MS/MS).

Statistical Methods

Definitions of Analysis Sets

Efficacy Analysis Set will include efficacy evaluable subjects who received at least 1 administration of the study drug and who has at least 1 appropriate tumor assessment data of Screening 2 and post-baseline.

Pharmacokinetic Analysis Set will include subjects who received at least 1 administration of the study drug and had at least 1 concentration data of tazemetostat.

Biomarker Analysis Set will include subjects who have conducted EZH2 gene mutation assessment at Screening 1.

Safety Analysis Set will include subjects who received at least 1 administration of the study drug.

Efficacy Analyses

This analysis will be performed on the Efficacy Analysis Set. All summary of efficacy will be conducted for each disease (cohort).

Primary Endpoint Analyses

Eisai Confidential Page 8 of 71

BOR will be summarized. The rate of subjects whose BOR is CR or PR is calculated as ORR, and its corresponding 2-sided exact 90% confidence intervals (CIs) using the method of Clopper–Pearson will also be calculated. A waterfall plot will be presented for the percent changes from baseline in the sum of the diameters of target lesions at post-baseline nadir.

Secondary Endpoint Analyses

- Analysis of PFS
 PFS will be summarized by Kaplan-Meier method using median with 95%CI.
- Analysis of DOR
 DOR will be summarized by Kaplan-Meier method in responders.
- Analysis of TTR
 TTR will be summarized by descriptive statistics in responders.

Pharmacokinetic Analyses

This analysis will be performed on the Pharmacokinetic Analysis Set. The plasma concentrations of tazemetostat will be summarized by timepoint.

Biomarker Analysis

This analysis will be performed on the Biomarker Analysis Set. The rate of the tumor EZH2 gene mutation will be calculated in each disease.

Safety Analyses

This analysis will be performed on the Safety Analysis Set. The number and percentage of subjects with all AEs and SAEs observed after first administration of study drug will be summarized and listed by system organ class (SOC), preferred term (PT), and severity in whole or each disease (cohort). Summary statistics will be presented for laboratory test values, vital signs, 12-lead ECG, and ECOG-PS. If needed, the changes from baseline will also be summarized.

Sample Size Rationale

In cohort 1, 8 efficacy evaluable FL patients with EZH2 mutation are required to detect lower limit of the 90% CI that exceed the 10% threshold in ORR, which is the primary endpoint of the study, with the expected ORR of 50% with power of approximately 80%.

In cohort 2, 13 efficacy evaluable DLBCL patients with EZH2 mutation are required to detect lower limit of the 90% CI that exceed the 10% threshold in ORR, which is the primary endpoint of the study, with the expected ORR of 40% with power of approximately 80%.

Eisai Confidential Page 9 of 71

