9.5.1.3 Efficacy Assessments

Efficacy assessment will be performed by investigator or subinvestigator based on "Revised response criteria for malignant lymphoma (IWG-2007)" (Cheson, et al., 2007). Overall response and best overall response (BOR) (best response recorded at the designated visits during the study) will be assessed. Perform the assessment below for tumor assessment.

CT scans will be performed at Screening 2, every 8 weeks from study drug administration up to first 32 weeks, then every 12 weeks and at discontinuation.

Eisai Confidential Page 42 of 71 FINAL: 29 Jan 2021

PET scans will be performed at Screening 2. If positive, perform when it is required to confirm CR as soon as possible or when clinically indicated.

If gastrointestinal disease is suspected, endoscopic examination will be performed at Screening 2. If exists, perform when it is required to confirm CR as soon as possible or when clinically indicated.

To evaluate bone marrow infiltration, a bone marrow aspiration or biopsy will be performed at Screening 2. If positive or indeterminate, perform when it is required to confirm CR as soon as possible or when clinically indicated.

Also, central review will be conducted by the Imaging Review Committee for CT and PET assessment. In addition, Efficacy and Safety Evaluation Committee (ESEC) will conduct central evaluation based on the review of Imaging Review Committee and other assessment / bone marrow infiltration evaluated by the investigator or subinvestigator, to determine the overall responses and the best overall response.

The primary endpoint and the secondary endpoint with regard to efficacy are defined as below, and will be evaluated by the result of ESEC review.

ORR:

The rate of subjects whose BOR is CR or PR.

PFS

Defined as the term between the date of administration of the first dose of the study drug and the date of the first event (PD or death whichever occurs first). The detail of the censoring rule for PFS will be described in the statistical analysis plan (SAP).

• DOR:

Defined as the term between the date of confirmation of the first response and the date of confirmation of the PD. The detail of the censoring rule for DOR will be described in the SAP.

TTR·

Defined as the term between the date of administration of the first dose of the study drug and the date of confirmation of the first response.

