9.7 Statistical Methods

All statistical analyses will be performed 1) after data cut-off for primary analysis or 2) after the study is completed and the database is locked and released. Data cut-off will be performed at Week 56 (after more than 12 months from the start of treatment to all subjects), or after the discontinuation of treatment before 12 months. Statistical analyses will be performed using SAS software or other validated statistical software as required. Details of the statistical analyses will be included in a separate SAP.

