## 5.4 Efficacy Analyses

All efficacy result will be summarized by disease (cohort) and overall. Results from central assessment by Efficacy and Safety Evaluation Committee and investigator assessment will be used.

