### 5.4.2 Secondary Efficacy Analyses

- Analysis of PFS

PFS will be summarized by Kaplan-Meier method using median with 95%CI. Kaplan-Meier curve will be provided. The number of event/censor (percentage) and reasons of censor will be also summarized.

- Analysis of DOR

DOR will be summarized by Kaplan-Meier method using median with 95% CI in responders. The number of event/censor (percentage) and reasons of censor will be also summarized.

- Analysis of TTR

TTR will be summarized using descriptive statistics in responders.

PFS will be calculated as:

End date for PFS – Date of administration of the first dose of study drug + 1 (day)

DOOR will be calculated as:

End date for DOOR – Date of the first response + 1 (day)

End date of PFS and DOOR is defined as the table below:

Situation	End Date for PFS and DOOR	Censored
Documented progression disease (PD) during the study	Date of the first assessment of the series of the tests that determined PD	No
Death during the study before PD	Date of death	No
No baseline assessments	Date of administration of the first dose of study drug	Yes
Treatment discontinuation without post-baseline tumor assessments	Date of administration of the first dose of study drug	Yes
Treatment discontinuation without documented PD or death with post-baseline tumor assessments	Date of last tumor assessment before discontinuation	Yes
New anticancer treatment started prior to disease progression	Date of last tumor assessment before start of new treatment	Yes
Death or PD after more than one missed tumor assessments	Date of the last tumor assessment before missed assessments	Yes
Subjects still on treatment without PD as of data cut-off	Date of last tumor assessment	Yes

TTR will be calculated as:

Date of first response – Date of administration of the first dose of study drug + 1 (day)

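### Does the 02 Dec 2020 limit on centrally read images leave the tail of the final ESEC-based PFS and DOR curves undefined?

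*Protocol*

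**What the plan says.** The Efficacy Assessments part of the protocol synopsis has the primary and secondary efficacy endpoints evaluated by ESEC, and limits the images sent for central review to those "which is obtained within 24 months after the last subject's enrollment (cut-off date: 02 Dec 2020". Protocol 9.5.1.3 gives the same instruction without a date: "Also, central review will be conducted by the Imaging Review Committee for CT and PET assessment".

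Protocol 9.7 foresees two analysis points. One follows the primary-analysis cut-off at Week 56. The other comes "after the study is completed and the database is locked and released". Both the synopsis and 9.5.1.3 leave the PFS and DOR censoring rules to the SAP.

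SAP 5.4 says: "Results from central assessment by Efficacy and Safety Evaluation Committee and investigator assessment will be used". In the end-date table of SAP 5.4.2, four rows matter here:

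- "Death during the study before PD" is an event at the date of death.
- Subjects who stop treatment without progression or death, but with post-baseline assessments, are censored at "Date of last tumor assessment before discontinuation".
- "Death or PD after more than one missed tumor assessments" is censored at the last assessment before the gap.
- "Subjects still on treatment without PD as of data cut-off" is censored at the last tumour assessment.

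No row carries a calendar date. SAP section 8 leaves data handling to the sponsor before database lock, and SAP section 9 places the derivation rules in separate documents.

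**The concern.** Some subjects were followed beyond 02 Dec 2020. The protocol dated 29 Jan 2021 still treats approval as a future event, and SAP 5.6.2 tabulates adverse events for follicular lymphoma subjects who stayed on study after approval. For them, progression visible only on later scans cannot become an ESEC event. Read literally, the table then allows three treatments of the tail:

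- **Reading A:** any scan extends follow-up, even if ESEC never read it. A subject with late site-evaluated progression is censored at that scan. Later deaths count.
- **Reading B:** only ESEC-read scans extend follow-up, but later on-study deaths still count, on a nearly empty risk set.
- **Reading C:** as B, but unread scans are classed as missed, so the missed-assessment row censors most later deaths.

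The natural comparator is a **common cut-off** (call it F): progression, deaths and censoring all stop at 02 Dec 2020. With 8 or 13 subjects planned, a single late death could decide whether a median is reported as a number or as not reached. The long responders sit in exactly this part of the curve.

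**Working it through.** **Dates.** The last enrolment date is not given. Counting 24 months back from 02 Dec 2020 implies about 02 Dec 2018. Adding 56 weeks (392 days) gives 29 Dec 2019, which is 339 days before the image limit, so the primary analysis is clear of it. From the limit to the date of SAP version 2.0 (31 May 2022) is 545 days. At one CT every 12 weeks, 545/84 = 6.5, or up to six unread scans per ongoing subject. This is an upper bound, because the SAP date is not a follow-up date.

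**Part of the curve that can move.** Every subject has about 24 months (731 days) of central reading available. On the protocol's schedule (weeks 8, 16, 24, 32, then every 12) the last CT in that window is week 104, at 728/30.4375 = 23.9 months. The one before is week 92, at 644/30.4375 = 21.2 months. All readings agree before about 21-24 months.

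**A constructed worst case (n = 8).** ESEC events fall at 5.5, 10.1 and 15.6 months. The other five subjects have last ESEC-read scans at 23.9, 23.9, 26.7, 29.4 and 29.4 months. The subject last read at 26.7 dies on study at month 36, after three unread scans.

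- After three events: 7/8 × 6/7 × 5/6 = 0.625.
- F and C: no further event, so 0.625 and median not reached.
- B: one at risk, 0.625 × (1 − 1/1) = 0, median 36 months.
- A: five at risk, 0.625 × (1 − 1/5) = 0.50.

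The ambiguity can therefore matter in one data set. It takes an on-study death without progression, after the limit.

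**Average size.** The simulation used 1,500 runs per scenario. Its assumptions are exponential PFS, 8-month accrual (24-32 months of follow-up at the limit), 10% of the event hazard being death before progression, and up to 17.9 further months on study (545/30.4375). Kaplan-Meier estimates at 36 months are compared with the assumed survival 0.5^(36/median):

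| n | median (months) | A | B | C | F | assumed truth |
|---|---|---|---|---|---|---|
| 13 | 12 | 0.204 | 0.171 | 0.180 | 0.189 | 0.125 |
| 13 | 18 | 0.356 | 0.297 | 0.316 | 0.335 | 0.250 |
| 13 | 24 | 0.450 | 0.378 | 0.403 | 0.424 | 0.354 |
| 13 | 36 | 0.583 | 0.516 | 0.540 | 0.560 | 0.500 |
| 8 | 12 | 0.206 | 0.182 | 0.188 | 0.197 | 0.125 |
| 8 | 18 | 0.348 | 0.305 | 0.316 | 0.327 | 0.250 |
| 8 | 24 | 0.454 | 0.406 | 0.419 | 0.434 | 0.354 |
| 8 | 36 | 0.584 | 0.531 | 0.545 | 0.567 | 0.500 |

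Relative to F, A is 0.9-2.6 points higher, B 1.5-4.6 lower and C 0.9-2.2 lower. With no deaths, B and C equal F, and A is 1.7-3.2 points higher.

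**Is the departure from F a bias?** Maximum follow-up at the limit is 24 + 8 = 32 months, so under F nobody is at risk at month 36. The F column is the last step of the curve carried forward. In all eight scenarios B and C lie closer to the assumed truth than F does. Delay in detecting progression at scheduled scans raises the target by only about 1 point and does not alter that. F cannot serve as the yardstick, and the lower values under B and C are not shown to be errors.

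**Against the noise.** The approximate binomial standard error is √(0.424 × 0.576/13) = 0.137 for n = 13 and √(0.434 × 0.566/8) = 0.175 for n = 8, both at a 24-month median. The differences of 1-5 points are well inside it.

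**The planned summary.** SAP 5.4.2 asks for medians with 95% CI, event and censoring counts and, for PFS, the curve. It asks for no 36-month rate. The median differs from F in 0.3-12.5% of simulated trials under A, 0.2-15.0% under B and 0-3.5% under C.

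**The case for a change.** The strongest case for a change is that the SAP is the only place where these rules can be settled, since the protocol defers to it. Naming the readers in SAP 5.4 does not fix the rows of the table. If ESEC-read scans set the censoring dates while later deaths remain events, subjects without events leave the risk set by 02 Dec 2020 and only deaths can follow, which is informative. Nor is a death always needed: a long responder who switches to commercial drug after the limit might be censored at a scan ESEC never saw. One sentence would close all this.

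Part of that stands. The table is silent on late deaths and late site-evaluated progression, and its cut-off is not tied to a date for the final analysis. The rest weakens on inspection:

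- In an ESEC analysis, the last assessment is the last one ESEC assessed. Reading A joins ESEC progression to site scan dates, and reading C calls scans missed that were performed. Neither is how an analyst would normally build the ESEC data set.
- Reading B needs an on-study death before progression. The protocol has no survival follow-up. Under 9.1.1.3 observation ends 30 (+7) days after the last dose or at new anti-tumour therapy, and the final observation is waived for subjects who leave the study for commercial drug.
- The evidence of follow-up after approval concerns the follicular cohort (8 planned). The documents show none for the 13 planned DLBCL subjects, where the expected response rate is 40% and long medians are less plausible.
- A sentence fixing the ESEC cut-off at 02 Dec 2020 without confining it to the final analysis would itself conflict with the Week 56 cut-off in protocol 9.7.

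**Conclusion.** No change to the plan is needed. What remains is an unwritten convention for the tail of two secondary endpoints, in one of two analyses and under one of two assessors. Protocol 9.5.1.3 also omits a date that the synopsis supplies, which is a clerical slip. Analysts would fill the gap sensibly from the synopsis date and the SAP's naming of ESEC as a source, and the derivation documents and pre-lock data-handling decisions are the ordinary place to record it.

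The primary response-rate analysis, PFS to about 21-24 months and the investigator-based curves are unaffected. The simulated shifts are about 1-5 points in an unplanned 36-month estimate, with no bias shown. A changed median occurs in at most 15% of simulated trials, and in under 1% in the most favourable scenario for each reading. These figures rest on assumptions the documents do not supply: exponential PFS, 8-month accrual, a 10% share of deaths and follow-up to the SAP date. If several on-study deaths without progression did occur after 02 Dec 2020, the convention chosen would need to be stated alongside the ESEC medians.
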